3.2 Eligibility

Participants must meet all the following criteria on screening examination to be eligible to participate in the study:

Inclusion

1. Age \geq 18 years old
2. Has self-reported sleep disturbance
3. Insomnia Severity Index (ISI) score of \geq 15 at screening
4. Interested in understanding more about the quality of their sleep and chose to use the Sip2Sleep product for sleep
5. Willingness to do a minimum of 1 week wash out of current OTC or other products for sleep (e.g. melatonin, anticholinergics)
6. Willingness to do a minimum of 1 week wash out of any cannabis products
7. Able to receive shipment of the product at an address within the United States
8. If taking prescription hypnotics (e.g. zolpidem, zaleplon, benzodiazepines) or other class of medication for sleep, must be on a stable dose for at least 4 weeks.
9. Able to read and understand English
10. Able to use a personal smartphone
11. Has and is able to use a personal health tracking wearable device (e.g., Apple Watch, Fitbit Smartwatch, Oura Ring, etc.)
12. Able to understand and provide informed consent
13. Able to complete study assessments over 5 weeks

Exclusion

1. Research participants who have no computer, smartphone, and internet access and/or do not use a computer or smartphone
2. Concomitant Therapies:
 - a. Participants taking daily prescription medication for sleep (for example, prescription hypnotics like zolpidem, zaleplon, benzodiazepines) not on a stable dose for at least 4 weeks
 - b. Participants receiving Cognitive Behavioral Therapy for Insomnia (CBTi)

- c. Participants receiving any investigational therapies or treatments
3. Other Illnesses or Conditions: Participants who have the following co-morbidities are excluded:
- a. Confirmed diagnoses of the following sleep disorders: Narcolepsy, Restless Leg Syndrome, Circadian Rhythm Disorders
 - b. Confirmed diagnosis of Sleep Apnea that is untreated or not well controlled
 - c. Current or prior psychotic disorder
 - d. Current or prior Substance Abuse Disorder
 - e. Current or prior cardiac dysrhythmias (for example, atrial fibrillation, supraventricular tachycardia)
 - f. Currently pregnant, planning to become pregnant in the next 1 month, or breastfeeding
 - g. Allergies or adverse reactions (for example, anxiety) to Montmorency tart cherry extract and/or Venetron®

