3.3 Duration of Participation and Overview of What is Expected from Participants

Participants will complete a 5-week study consisting of screening assessments, baseline scales and surveys, objective digital measure, 2 weeks of product use (1 week on - 1 week off - 1 week on), scales and surveys, and end of study assessments and surveys. This is a remote observational study that will use the People Science app-based data collection platform Consumer Health Learning and Organizing Ecosystem (CHLOE) for study participants to report their assessments and collect objective sleep data from personal wearable devices. Participants will receive the study product during the baseline period. Demographic and medical history data will be collected for the study.

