4.0 STUDY ACTIVITY CALENDAR

Table 4.1 Study Calendar

Protocol Activities	Screening ^a	Study Duration ^b				
		Baseline	Product Use ^c	No Product Use	Product Use ^c	End of Study
Week	Up to 1 Week	Week 1	Week 2	Week 3	Week 4	
Day	Day -7 to -1	Day 1	Day 8	Day 15	Day 22	Day 29
Informed Consent	X					
Demographics	X					
Medical History	X					
Insomnia Severity Index	X	X	X	X	X	X
Eligibility	X					

Daily Objective Data Collection and Surveys ^d		X	X	X	X	X
Use of Study Product			X		X	
Generalized Anxiety Disorder-7		X	X	X	X	X
Experience Survey						X

- a. Screening to occur within 7 days prior to Baseline (Day 1)
- b. Planned duration of study is 4 weeks
- c. Participants to consume Sip2Sleep[®] product 30-60 minutes prior to lying down in bed.
- d. Participants will complete daily surveys to review objective data from wearable device collection and answer questions about their prior night’s sleep quality and level of alertness since waking.

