6.0 STUDY PROCEDURES

6.1 Study Overview

[figure not shown]

Figure 1. Study Design

Upon enrollment, the study assessments can be accessed via CHLOE mobile app available on Apple iOS and Android devices as well as any web browser. The participant's activities are as follows:

Screening (Day -7 to Day -1):

- Informed Consent
- Complete demographic and medical history data intake.
- Screening Insomnia Severity Index (ISI) assessment.
- Provide preferred shipment address for product shipment during Baseline.

Baseline Period (Day 1 to Day 7):

- Complete Insomnia Severity Index and Generalized Anxiety Disorder-7 (Day 1 only).
- Begin discontinuation of non-prescription products used for sleep.
- Begin nightly use of personal health tracking wearable device through Day 28.
- Complete daily survey to review objective data (sleep duration and sleep latency) from wearable device collection and answer questions about their prior night's sleep quality and level of alertness since waking.
- Receive shipment of study product and instructions for use.

Product Use Period (Day 8 to Day 14):

- Complete Insomnia Severity Index and Generalized Anxiety Disorder-7 (Day 8 only).
- Continue nightly use of personal health tracking wearable device through Day 28.
- Complete daily surveys to review objective data (sleep duration and sleep latency) from wearable device collection and answer questions about their prior night's sleep quality and level of alertness since waking.
- Administer nightly dose of study product 30-60 minutes prior to lying down in bed through Day 14.

No Product Use Period (Day 15 to Day 21):

- Complete Insomnia Severity Index and Generalized Anxiety Disorder-7 (Day 15 only).
- Continue nightly use of personal health tracking wearable device through Day 28.
- Complete daily surveys to review objective data (sleep duration and sleep latency) from wearable device collection and answer questions about their prior night's sleep quality and level of alertness since waking.

Product Use Period (Day 22 to Day 28):

- Complete Insomnia Severity Index and Generalized Anxiety Disorder-7 (Day 22 only).
- Continue nightly use of personal health tracking wearable device through Day 28.
- Complete daily surveys to review objective data (sleep duration and sleep latency) from wearable device collection and answer questions about their prior night's sleep quality and level of alertness since waking.

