- Administer nightly dose of study product 30-60 minutes prior to lying down in bed through Day 28.

End of Study (Day 29):

- Complete Insomnia Severity Index and Generalized Anxiety Disorder-7.
- Complete surveys to review objective data (sleep duration and sleep latency) from wearable device collection and answer questions about their prior night's sleep quality and level of alertness since waking.
- Complete Experience Survey.

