12.3 Participant Characteristics

Research equity

This research has no direct exclusions related to gender. There are also no direct exclusions related to race or ethnicity.

Vulnerable Populations

Pregnancy and lactation are exclusions due to the unknown risks of product use to fetuses and newborns.

There are exclusions for individuals with specific sleep diagnoses that require medical intervention.

Volunteers with impaired decision-making capacity are excluded.

Volunteers unable to personally provide informed consent (including but not exclusive of inability to speak and read English, hearing or sight impaired, etc.) will be excluded from participating in this research.

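### The 1-month pregnancy-planning exclusion can expire before the last product dose, which falls up to 34 days after screening

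*Combined protocol and SAP*

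**What the plan says.** Section 3.2, exclusion 3f, excludes people who are "Currently pregnant, planning to become pregnant in the next 1 month, or breastfeeding". The same section fixes when this is judged: "Participants must meet all the following criteria on screening examination to be eligible to participate in the study". Table 4.1 marks the eligibility check in the screening column only.

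Footnote a to Table 4.1 sets the screening window ("Screening to occur within 7 days prior to Baseline (Day 1"), and Section 6.1 places screening on Day -7 to Day -1. Product is taken in two blocks, Days 8 to 14 and Days 22 to 28. For the second block the instruction is "Administer nightly dose of study product 30-60 minutes prior to lying down in bed through Day 28".

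The reason for the exclusion is in Section 12.3: "Pregnancy and lactation are exclusions due to the unknown risks of product use to fetuses and newborns".

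On overall length, Section 3.3 says "Participants will complete a 5-week study consisting of screening assessments" and other components. Inclusion criterion 13 and Section 12.5 also use a five-week horizon. Footnote b to Table 4.1 gives four weeks, which is the period from Day 1.

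**The concern.** The look-ahead runs from the day the question is answered, but the exposure it guards against runs to a fixed study day. When screening is early, the first can end before the second.

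Take a person screened on Day -7 who intends to start trying to conceive 32 days later, which is Day 26. She can truthfully say that she has no such plan within a month, is enrolled, and is still scheduled to take product on the nights of Days 26, 27 and 28.

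What is at stake is participant protection, not inference. The study is remote and self-administered. The protocol text describes no pregnancy test, contraception requirement, re-check before dosing, or rule to stop on becoming pregnant. The answer at screening is therefore the only pregnancy safeguard it describes.

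**Working it through.** **Inputs**

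- Screening day: Day -7 to Day -1 (Section 6.1; Table 4.1, footnote a).
- Product nights: Days 8 to 14 and Days 22 to 28, 14 nights in all (Section 6.1).
- Look-ahead: 1 month from screening (exclusion 3f). Its length in days is not defined, so 28, 30 and 31 days are all shown.
- Day numbering: no Day 0. Screening at most 7 days before Day 1 and starting on Day -7 is consistent only with this numbering.

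**The plan's own figure.** Seven screening days (Day -7 to Day -1) plus 28 study days (Day 1 to Day 28) is 35 days, or 5 weeks. This reproduces the five-week participation in Section 3.3.

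**Time from screening to the last dose.** For screening on Day -s, the elapsed time to Day 28 is s + 27 days: s days to Day 1, then 27 more. For Day -7 this is 7 + 27 = 34 days. For Day -1 it is 1 + 27 = 28 days.

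**Uncovered nights.** A product night is uncovered if it falls more than m days after screening, where m is the length of the month. All such nights lie in the second product week, so the count is max(0, s + 27 - m).

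| Screening day | Days to last dose | 31-day month | 30-day month | 28-day month |
|---|---|---|---|---|
| -7 | 34 | 3 | 4 | 6 |
| -6 | 33 | 2 | 3 | 5 |
| -5 | 32 | 1 | 2 | 4 |
| -4 | 31 | 0 | 1 | 3 |
| -3 | 30 | 0 | 0 | 2 |
| -2 | 29 | 0 | 0 | 1 |
| -1 | 28 | 0 | 0 | 0 |

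For screening on Day -7, -6 or -5, no month length closes the gap.

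**Which month length is typical.** Counting a calendar month from every date in 2022 to 2025 (1,461 dates, each treated as Day -7) gives 3 uncovered nights on 841 dates, 4 on 500, 5 on 33 and 6 on 87. So 3 or 4 nights is the result on (841 + 500)/1,461 = 92% of dates, and 6 nights is uncommon.

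**Sensitivity to Day 0.** If a Day 0 did exist, Day -7 to Day 28 would be 35 days, and 4, 5 or 7 nights would be uncovered. The footnote points to 34 days, the smaller figure.

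**After the change.** A look-ahead of at least 34 days from screening, or one defined as ending with the Day 28 dose, leaves 0 uncovered nights for every screening day.

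**The case against.** The strongest objection is about weight; the day count is not in dispute.

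*The 3 to 6 nights are a worst case.* True. If screening days were evenly spread (an assumption), the average would be (4 + 3 + 2 + 1)/7 = 1.4 nights with a 30-day month and (3 + 2 + 1)/7 = 0.9 with a 31-day month.

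*Hardly anyone would be affected.* Probably so. The documents give no rate of planned conception, so the following is an illustration only. Suppose all 80 possible enrollees (Section 9.1) are counted and 1% to 10% would begin trying at a uniformly distributed time in the next 91 days. With a 30-day month and even screening, the expected number is 80 × (0.01 to 0.10) × 1.43/91, or about 0.01 to 0.13 people. If everyone were screened on Day -7, it is 80 × (0.01 to 0.10) × 4/91, or about 0.04 to 0.35. This stands and limits the importance of the point.

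*One month is a fair rounding of the four-week study.* Counted from Day 1 it does cover Day 28. But the four weeks start at Day 1 and the question is answered up to 7 days earlier. This explains how the mismatch could arise; it does not remove it.

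*Section 12.3 mentions pregnancy and lactation, not planned pregnancy.* That is right, and both are excluded outright at screening. Still, a clause about planned pregnancy can only serve the same purpose, and no other reason is given for it.

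*A question about intentions cannot catch unplanned pregnancy, however long its window.* Correct. The change makes the criterion consistent with its purpose and does no more than that.

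*The pre-screening questionnaire and consent are not available here.* They might contain further safeguards. Equally, if the question is asked only in the pre-screening questionnaire (Section 5.1), the answer could predate Day -7 and the gap would be longer. Neither can be settled from the documents.

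**Conclusion.** The concern holds. The last scheduled dose is up to 34 days after the only stated eligibility check, and the exclusion looks ahead 1 month. At most 3, 4 or 6 of the 14 product nights fall outside a 31-, 30- or 28-day month, with 3 or 4 the usual worst case. With a 31-day month the gap is gone for screening on Day -4 or later; with a 30-day month, on Day -3 or later.

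This rests on three readings: there is no Day 0, exclusion 3f is answered within the Day -7 to Day -1 window, and no re-check takes place before dosing, as none is described. The practical exposure is small. The change should be made because a safety criterion falls short of its stated purpose and correcting it costs almost nothing.

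**What to change.** Reword the planning clause of exclusion 3f in study time, so that it excludes anyone planning to become pregnant at any point up to and including the last scheduled product night (Day 28), whatever the day of screening. If a fixed interval is preferred, it must be at least 34 days from screening; five weeks would do and matches inclusion criterion 13. If the question is first asked before Day -7, a fixed interval must be lengthened to match, which is a reason to prefer the wording tied to Day 28.

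Use the same wording in the pre-screening questionnaire and the consent. Whether to add a margin after the last dose is for the sponsor and the IRB to decide.

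The cost is one phrase in the criterion, the matching screening question, and a very small number of additional screen failures.

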3.3 Duration of Participation and Overview of What is Expected from Participants

Participants will complete a 5-week study consisting of screening assessments, baseline scales and surveys, objective digital measure, 2 weeks of product use (1 week on - 1 week off - 1 week on), scales and surveys, and end of study assessments and surveys. This is a remote observational study that will use the People Science app-based data collection platform Consumer Health Learning and Organizing Ecosystem (CHLOE) for study participants to report their assessments and collect objective sleep data from personal wearable devices. Participants will receive the study product during the baseline period. Demographic and medical history data will be collected for the study.

3.4 Participant Recruitment

Participants will be recruited through professional networks and email/social media channels. Advertisement will be in digital format and will link to a study landing page to enable sign up.

4.0 STUDY ACTIVITY CALENDAR

Table 4.1 Study Calendar

Protocol Activities	Screening ^a	Study Duration ^b				
		Baseline	Product Use ^c	No Product Use	Product Use ^c	End of Study
Week	Up to 1 Week	Week 1	Week 2	Week 3	Week 4	
Day	Day -7 to -1	Day 1	Day 8	Day 15	Day 22	Day 29
Informed Consent	X					
Demographics	X					
Medical History	X					
Insomnia Severity Index	X	X	X	X	X	X
Eligibility	X					

Daily Objective Data Collection and Surveys ^d		X	X	X	X	X
Use of Study Product			X		X	
Generalized Anxiety Disorder-7		X	X	X	X	X
Experience Survey						X

- a. Screening to occur within 7 days prior to Baseline (Day 1)
- b. Planned duration of study is 4 weeks
- c. Participants to consume Sip2Sleep[®] product 30-60 minutes prior to lying down in bed.
- d. Participants will complete daily surveys to review objective data from wearable device collection and answer questions about their prior night’s sleep quality and level of alertness since waking.

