1.0 OBJECTIVES AND ENDPOINTS

Objectives	Endpoints/ Measurements
Primary Objective	

 To observe the effect of the Sip2Sleep® product on sleep quality for participants with self-reported sleep disturbance 	
 Change in average sleep quality score by 1 point as measured by daily 10-point visual analogue rating scale (VAS) from baseline and 1 week of no product use
Secondary Objectives	

 To assess the effect of Sip2Sleep® product on symptoms of sleep disturbance To assess the effect of Sip2Sleep® product on anxiety To assess the effect of Sip2Sleep® product on the level of alertness during the daytime 	
 Change in Insomnia Sleep Index (ISI) by 4.5 points from baseline and 1 week of no product use Change in Generalized Anxiety Disorder-7 (GAD-7) by 4.5 points from baseline and 1 week of no product use Change in average level of alertness during the daytime score by 1 point as measured by daily 10-point visual analogue rating scale (VAS) from baseline and 1 week of no product use
Exploratory Objectives	

 To observe the change in sleep duration via personal health tracking wearable device To observe the change in sleep latency via personal health 	
 Change in average nightly sleep duration as measured via personal health tracking wearable device from baseline and 1 week of no product use Change in average nightly sleep

tracking wearable device
 
3. To identify improvements for future participant-centered study designs using feedback
	
latency as measured via personal health tracking wearable device from baseline and 1 week of no product use
 
3. Assessment of patient satisfaction survey of study experience including design and use of app-based data collection tools

---	--

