Insomnia Sleep Index (ISI) is a brief self-report instrument measuring the patient's perception of both nocturnal and diurnal symptoms of insomnia during the past two weeks. The ISI comprises seven items assessing the perceived severity of difficulties initiating sleep, staying asleep, and early morning awakenings, satisfaction with current sleep pattern, interference with daily functioning, noticeability of impairment attributed to the sleep problem, and degree of distress or concern caused by the sleep problem. Each item is rated on a five-point scale and the total score indicates the severity of insomnia, with a range of possible scores from 0-28. A score higher than 14 has been indicated to be the optimal cut-off for insomnia as a disorder. The ISI has been widely used in clinical and research settings as it is brief and easy to administer, and can provide valuable information for diagnosis and treatment planning. Research has found that the ISI is sensitive in detecting changes in the patient's perception of treatment outcome, and a good degree of convergence exists between the patient and the clinician's evaluation of insomnia severity.^{13,14}

Generalized Anxiety Disorder-7 (GAD-7) is a self-reported anxiety survey utilized in primary care consisting of a 7-item anxiety scale. The instrument is well supported to use in a general population and normative data can be used to compare a subject's GAD-7 score with those determined from a general population reference group, with evidence of significant reliability and validity with congruent agreement in self-reported and interviewer-administered versions of the

scale. GAD and Depression symptoms frequently occur together, but previous studies have supported via factor analysis that this measure can detect GAD and depression as distinct dimensions.¹⁵ This measure will be used in combination with other scales to observe self-reported effects on sleep disturbances and insomnia, such as anxiety or other psychiatric disorders.

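### The only baseline-period ISI and GAD-7 are taken on Day 1, soon after selection on the ISI and before other sleep products are washed out; the Day 8 scores should be analysed alongside them

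*Combined protocol and SAP*

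**What the plan says.** Section 1.0 sets two secondary endpoints on these scales: "Change in Insomnia Sleep Index (ISI) by 4.5 points from baseline and 1 week of no product use" and "Change in Generalized Anxiety Disorder-7 (GAD-7) by 4.5 points from baseline and 1 week of no product use". Inclusion criterion 3 in Section 3.2 requires an "Insomnia Severity Index (ISI) score of" 15 or more at screening, so the scale that selects people is also an outcome. Footnote a of the calendar in Section 4.0 places selection close to baseline: "Screening to occur within 7 days prior to Baseline (Day 1".

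In Section 6.1 the Baseline Period runs from Day 1 to Day 7. Its only ISI and GAD-7 are on Day 1. The same period carries the instruction "Begin discontinuation of non-prescription products used for sleep". The next scores come on the first day of product use: "Complete Insomnia Severity Index and Generalized Anxiety Disorder-7 (Day 8 only". The product is taken at night, but the order of the Day 8 questionnaires and the first dose is not stated.

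Section 2.2 describes the ISI as covering "both nocturnal and diurnal symptoms of insomnia during the past two weeks". Section 9 names no assessment day as the ISI or GAD-7 baseline. Day 1 is the reading that follows from the calendar and Section 6.1.

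**The concern.** The study has no concurrent control, so a change from baseline on these scales will be read as an effect of the product. Two other things can move the scores after Day 1.

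- **Stopping other products.** The Day 1 scores describe people who may still be using other sleep aids. The end-of-study scores describe people who have stopped. This affects both scales, and the shift could go either way.
- **Residual regression to the mean.** People enter because their ISI was high. If Day 1 still carries part of that selected high value, the ISI will drift down afterwards without any treatment. This acts directly on the ISI. GAD-7 is not a selection variable and is touched only through its correlation with the ISI.

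At stake is what the secondary results can support: a significant fall from Day 1 need not be due to the product.

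**Working it through.** **1. The plan's own figures (Section 9.1).** SD of the VAS difference = 2 × √(2 × (1 − 0.50)) = 2.0. For a difference of 1, two-sided alpha 0.05 and 90% power, a paired t-test needs 44. Dividing by the signed-rank efficiency of 3/π gives 44 / 0.955 = 46.1, so 47. The figure reproduces, with power of 90.6% at 47. For the ISI and GAD-7, 4.5 points with a change SD of 5 gives power above 99.9%. If 5 is the SD of each score and the correlation is zero, power is 98.6%. Sample size is therefore not the issue; n = 47 and SD 5 are carried forward.

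**2. Nights behind each ISI.** Inputs: 14-night recall (Section 2.2), screening on Day −k with k = 1 to 7 and no Day 0 (Section 4.0), discontinuation starting no earlier than Day 1 (Section 6.1). Questionnaires are assumed to be completed before that night. Screening covers nights −(k+14) to −(k+1), so it shares 14 − k nights with Day 1 and 7 − k with Day 8.

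| ISI on | Nights recalled | Shared with screening ISI | After discontinuation starts |
|---|---|---|---|
| Day 1 | −14 to −1 | 7 to 13 | 0 |
| Day 8 | −7 to 7 | 0 to 6 | at most 7 |
| Day 22 | 8 to 21 | 0 | 14 (7 on product) |
| Day 29 | 15 to 28 | 0 | 14 (7 on product) |

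The figure for Day 8 is a maximum, because Section 6.1 says only that discontinuation begins within the week.

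**3. Residual regression to the mean, ISI.** Under a normal model, spurious fall = (correlation of screening with baseline score − correlation of screening with Day 29) × excess of the selected mean over the applicant mean. Assumptions, none of them in the documents:

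- Applicant mean ISI 12 to 16, and applicant SD 5 (borrowed from the planning SD).
- Correlation with screening 0.80–0.90 at Day 1, 0.75–0.80 at Day 8 and 0.60–0.70 at Day 29.

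With a cut at 14.5, the excess is 5.7, 4.3 and 3.1 points for applicant means of 12, 14 and 16.

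- From Day 1: (0.80 − 0.70) × 3.1 = 0.3, up to (0.90 − 0.60) × 5.7 = 1.7.
- From Day 8: (0.75 − 0.70) × 3.1 = 0.15, up to (0.80 − 0.60) × 5.7 = 1.1.
- If the correlation with screening does not decay after Day 1, the fall is 0 from either day.

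The ranges are therefore 0 to 1.7 from Day 1 and 0 to 1.1 from Day 8. More extreme assumptions (applicant mean 10, correlation falling by a factor of 0.9 per week) give 2.4 and 1.7.

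**4. Against significance and the target.** With n = 47 and a change SD of 5, the smallest significant mean change is about 2.013 × 5 / √47 = 1.47 points. With no product effect, a non-product shift of 0.5, 1.0, 1.5 or 2.0 points gives p<0.05 with probability 10%, 26%, 50% or 75%. The 1.7-point upper value is 1.7 / 4.5 = 38% of the target.

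**5. Washout.** The documents give neither the share of participants using other products nor the size of any shift on stopping them. No figure can be computed.

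**The case against.** Day 1 is itself a re-measurement after selection, so some regression has already happened before it. What remains rests entirely on assumed correlations and may be zero. That stands, and it is why the range starts at 0.

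A reader might infer that Day 8 is a clean baseline and should simply replace Day 1. The documents do not support that. At least half of the Day 8 ISI recall precedes washout, and completion before the first dose is implied rather than stated. If stopping other aids worsens sleep for a time, the Day 8 score would carry that worsening and Day 29 would not, so change from Day 8 could overstate the benefit. Nor does Day 8 reliably halve the regression: at the upper end it keeps 1.1 of 1.7 points, about two-thirds.

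It is also tempting to say that change from Day 1 flatters the product. For the ISI, regression would do so, but the washout effect may oppose it, and the net direction is unknown.

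Finally, Section 1.0 offers a second comparator, the week without product. It is later and fully after discontinuation, but the ISI closing that week (Day 22) recalls seven product nights as well as seven without, so it does not settle the matter.

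**Conclusion.** The point holds as a limit on how the secondary ISI and GAD-7 changes can be interpreted. The timing facts come from the documents; the night counts follow from them, given morning or daytime completion. The washout problem needs no correlation assumption, though its size is unknown and it arises only in people who were using other products. The regression component is a possibility confined mainly to the ISI. It could be enough to produce a significant change from Day 1, but it does not by itself approach 4.5 points.

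A reader might infer that the primary endpoint shares the problem. It does not in this form: the VAS is averaged over daily scores, so as Sections 1.0 and 6.1 read, its baseline is the washout week itself. That also shows the mismatch, since the ISI and GAD-7 baseline precedes the week that serves as baseline for the VAS.

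**What to change.** In Sections 1.0, 4.0 and 9.6:

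- State that the Day 8 ISI and GAD-7 are completed before the first product use, and label them the end-of-baseline assessment. This matches the week used for the VAS baseline.
- Report the ISI and GAD-7 change from Day 8 alongside the change from Day 1.
- Report the Day 1 to Day 8 change as pre-product drift.
- State that a change seen only from Day 1 will not be attributed to the product.

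The cost is wording and one more contrast per scale. No visit, instrument or participant is added, because the Day 8 scores are already collected. Both baselines need to be shown because neither is clean. Fixing this before the data are seen also removes the freedom to choose a baseline afterwards, which the silence of Section 9 now allows.
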